4.2.2 Secondary Study Endpoints

The secondary study endpoint will be the evaluation of PTSD symptom severity using DSM-5 PTSD symptoms measured with the Clinician-Administered PTSD Scale for DSM-5 (CAPS) Past Week version at the Post-treatment assessment. In addition to the experimental primary and secondary end points, there will be primary safety endpoints. Subjects will not receive any stimulation beyond what they consider highly annoying to them. Subjects will be thoroughly screened prior to starting the fMRI component of the study to make sure that they have no metal implants of any kind that would be considered a hazard to their health in the fMRI. We will use a metal detector to screen all subjects and make sure that they carry no metals to the

scanner room. Pregnancy tests will be done for all female participants with child-bearing potential prior to the initiation of the experiment to rule out pregnancy. If pregnancy is suspected, subjects will not be allowed to participate in the study. If any excess movement by the subjects is observed (which could be indicative of discomfort), the study staff will check with the subjects and inquire whether they would like to stop the experiment. After estrogen administration, all subjects will be monitored for any adverse events. This risk, however, is low given that estrogen is a commonly used agent with known side effect profiles, a component of many oral and non-oral birth controls and given only for 5 total 2mg/ dose twice weekly doses in the study. Reasons for study discontinuation for any participants who stop the treatments or study prematurely will also be recorded and reported.

5 Study Enrollment and Withdrawal

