9.4.6 Baseline Descriptive Statistics

We will perform descriptive statistics prior to testing our hypotheses. These statistics will include means (or frequencies and proportions for categorical variables), standard deviations, skewness and kurtosis, and odds-ratios. Variables with distributions violating assumptions of normality will be transformed. If this fails to improve the normality of the distribution, distribution-free statistics will be employed. This study has baseline, post-treatment, and two follow-up assessments, creating clustered data due to repeated measures. Thus, we will use established methods for such study designs to examine treatment differences, including the two most popular approaches for longitudinal data modeling: the generalized estimating equations (GEE) and linear mixed-effects model approach (LMM). We will apply these models for both the intent-to-treat and completer analyses. Inference based on GEE or LMM is valid provided that missing data are non-informative or "missingness" does not depend on the value of the unobserved outcome. Although missing data in many studies in mental health research are non-informative, we will perform sensitivity analyses to ensure that this is the case. In particular, we will entertain both parametric and semi-parametric models that assume some missingness mechanism and compare estimates obtained from such models with those from GEE and LMM. Such analyses will inform us whether the non-informative missingness assumption is violated and if so, to what extent. If the non-informative missingness assumption is deemed to be severely violated, we will report treatment effects using the methods that account for informative missingness.

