9.4.9 Efficacy Review

Interim analyses will not be conducted. All analyses will be conducted after breaking the blind at the end of the study unless a blinded review is requested by the DSMB.

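### Section 9.4.6 does not fix which estimate carries the CAPS conclusion: an uncheckable missing-data judgement, by default made unblinded, can move reporting to unnamed methods

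*Combined protocol and SAP*

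**What the plan says.** Section 9.4.6 describes data collected at baseline, post-treatment and two follow-ups. It names both GEE and a linear mixed model (LMM), makes neither the main analysis, and gives no working correlation, weighting or covariance structure. CAPS is not named there, but section 9.3 tests Hypothesis 2 on CAPS at these same visits. Section 4.2.2 makes CAPS ("Past Week version at the Post-treatment assessment") the secondary endpoint.

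On missing data, section 9.4.6 proceeds in four steps:

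- Validity: "Inference based on GEE or LMM is valid provided that missing data are non-informative", restated as missingness that "does not depend on the value of the unobserved outcome".
- Purpose of the extra models: "we will perform sensitivity analyses to ensure that this is the case".
- What comparing them with GEE and LMM will show: "Such analyses will inform us whether the non-informative missingness assumption is violated and if so, to what extent".
- Consequence: "If the non-informative missingness assumption is deemed to be severely violated, we will report treatment effects using the methods that account for informative missingness".

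Section 9.4.9 adds: "All analyses will be conducted after breaking the blind at the end of the study unless a blinded review is requested by the DSMB". The pointers in sections 9.4.3 and 9.4.10 lead to sections 10.1 to 10.3 and 10.4.6. Section 10 concerns source documents, so they supply no further rule.

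**The concern.** A sensitivity analysis shows how far a result depends on an assumption. It cannot confirm or refute the assumption when the evidence lies in values nobody observed. Two models can fit the observed CAPS scores equally well and imply different treatment effects, because they differ only in what they assume about the missing scores. Section 9.4.6 nevertheless treats the comparison as a finding about the missingness, and lets that finding change how the effect is reported. There is no threshold, no named alternative and no named decision-maker, and by default the arm results are visible.

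Section 9.5 describes the clinical aim as a preliminary proof of concept whose results will inform later power calculations. Which estimate is carried forward therefore matters, even for a secondary endpoint.

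The lesser issue is the validity condition. Missingness that does not depend on the unobserved outcome (missing at random, MAR) suffices for a correctly specified likelihood LMM. Unweighted GEE in general needs missing completely at random (MCAR), or else a correctly specified working covariance.

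**Working it through.** The plan gives no figure for the clinical measures, so there is none to reproduce.

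**Inputs.** From the documents: 80 randomised to two groups (taken as 40 per arm), alpha 0.05 (taken as two-sided) and about 20% dropout (section 9.5). Assumed, because the documents give no value: CAPS SD 10, baseline to post-treatment correlation 0.6, true difference 6 (placebo minus estradiol), and departures from MAR of delta = 3, 5 or 10 CAPS points. The share missing at post-treatment is taken as 20% (all dropout before Visit 12) or 8%.

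**Why the data cannot decide.** If unseen scores in one arm differ by delta from their MAR prediction, that arm's mean moves by (share missing) x delta and the fit to the observed scores is unchanged. With 20% missing, delta = 5 moves the difference by 0.2 x 5 = 1.0 point, and delta = 10 moves it by 2.0.

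**Size against the standard error.**
- Residual SD after baseline adjustment: 10 x sqrt(1 - 0.6^2) = 8.
- Observed per arm: 40 x 0.8 = 32. SE = 8 x sqrt(2/32) = 2.0 (simulated mean 2.01).
- Expected z at a true difference of 6: 6/2.0 = 3.0. A 1.0-point shift is 0.5 SE.
- Placebo missing scores 5 worse, non-significant becomes significant: Phi(-1.04) - Phi(-1.54) = 14.9% - 6.2% = 8.7%.
- Placebo missing scores 5 better, significant becomes non-significant: Phi(-0.54) - Phi(-1.04) = 29.5% - 14.9% = 14.6%.
- No true difference, always taking the favourable result: 2.5% + [1 - Phi(1.46)] = 2.5% + 7.2% = 9.7%.

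**Simulation of the same model**, which also allows for the sampling variation in the share missing. Ranges over delta cover missing scores assumed worse or better.

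| Share missing; who departs | Verdict changes, delta 3 | delta 5 | delta 10 | False positives if the favourable result is always reported, over the three deltas |
|---|---|---|---|---|
| 20%; placebo only | 6-9% | 9-17% | 14-38% | 7-18% |
| 20%; both arms alike | about 3% | about 5% | about 10% | 5-8% |
| 8%; placebo only | 2-3% | 3-5% | 6-13% | 6-9% |

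When both arms depart alike, the shift is delta times the chance difference in missing shares, whose SD is sqrt(2 x 0.2 x 0.8/40) = 0.089. At delta = 5 that is about 0.45 point. With 8% missing, SE = 8 x sqrt(2/36.8) = 1.87 and the shift at delta = 5 is 0.4 point.

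**GEE condition.** This simulation assumed SDs of 9 to 11 and a true difference of 6, with dropout depending on the last CAPS score. Exchangeable GEE gave 5.8-6.0 at post-treatment, and LMM gave 6.0. Exchangeable GEE and unstructured LMM disagreed on p<0.05 in 0.4-3.0% of trials of 40 per arm, no more than two LMMs with different covariance structures did (2.1-4.8%). Independence GEE without baseline adjustment was clearly biased when dropout differed by arm. With 7-9% lost by post-treatment it gave 5.6 (dropout related to CAPS in one arm) or 5.1 (opposite directions). With 18-22% lost it gave 5.0 or 4.0. Bias was nil when dropout worked alike in both arms, and nil at post-treatment with baseline CAPS as a covariate.

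**The case against.** The strongest defence is that planning sensitivity analyses is good practice, that the endpoint is secondary and exploratory, and that the text can be read as adding a result. Much of this stands, and it limits the point.

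- A reader might infer that the GEE or LMM estimate would be suppressed. The text does not say so. It leaves open which estimate then carries the conclusion.
- A reader might infer a deliberate choice made with results in view. Section 9.4.9 is a general statement on the timing of analyses, not written about missing data, and it allows a blinded review if the DSMB asks. Unblinded is only the default.
- The placebo-only figures with 20% missing are the unfavourable end. Section 9.5 does not place its dropout before Visit 12. Participants lost before a first dose leave the modified intent-to-treat set (section 9.3). The final evaluation for those who stop treatment (section 5.7.2) may recover some CAPS scores, though its content is not stated. A departure of 10 points is 10/8 = 1.25 residual SDs.
- The plan specifies no formal test for informative missingness, so how often the switch would be triggered cannot be estimated. The false-positive column is a bound, not a forecast.
- A reader might take the GEE sentence to mean that the CAPS result will be biased. That needs an independence working correlation, no baseline adjustment and dropout that differs by arm. The plan states none of these.

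What remains is the rule itself: its trigger cannot be observed, its criterion is absent and its replacement is unnamed. None of the points above supplies these.

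**Conclusion.** The point holds in a limited form. Section 9.4.6 assigns sensitivity models a task they cannot perform and lets the outcome alter how the Hypothesis 2 effect is reported, without fixing the main estimate. At an assumed 5-point departure the significance verdict changes in roughly 3% to 17% of trials, depending on how many scores are missing and whether one or both arms depart. These figures rest on the assumed SD, correlation, true difference and departures, none of which the documents give. The GEE wording is an error of statement with a usually small effect. The primary BOLD and SCR endpoints and their power statement are not touched. The plan should be corrected, but the trial's main inference does not depend on it.

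**What to change.** Amend section 9.4.6 before unblinding.

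1. Replace the last sentence with: 'A prespecified informative-missingness sensitivity analysis (for example delta-adjusted, applied by arm and in both arms, over a stated range of delta) will always be reported beside the main result and will not replace it.' Delete the statements that such analyses will ensure, or inform the team whether, missingness is non-informative.
2. Name one main CAPS analysis: a likelihood-based mixed model with arm by visit, baseline CAPS Past Week (collected at Visit 1) as a covariate and a stated covariance structure, on the modified intent-to-treat set, with the post-treatment contrast as the secondary endpoint. Sections 7.1.3 and 9.6.1 do not say which CAPS version defines the randomisation severity stratum. If it is not Past Week, add the stratum to the model.
3. Limit the validity sentence to that model. Keep any GEE as supportive, either inverse-probability weighted or stated to require MCAR.

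The study statistician should choose the covariance structure and delta range and fix both in advance. The section pointers in 9.4.3 and 9.4.10 can be corrected at the same time.

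The cost is SAP wording and one planned sensitivity analysis, with no change to data collection. The downside is that any other informative-missingness model could then be reported only as exploratory.

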9.4.7 Planned Interim Analysis

Not applicable

9.4.8 Safety Review

See above re safety monitoring, reporting and DSMB including individual participant and study halting guidelines.

9.4.9 Efficacy Review

Interim analyses will not be conducted. All analyses will be conducted after breaking the blind at the end of the study unless a blinded review is requested by the DSMB.

9.4.10 Multiple Comparison/Multiplicity

As noted above, the study has baseline, post-treatment, and two follow-up assessments, creating clustered data due to repeated measures. We describe the plan of analysis and adjustments in section 10.4.6.

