4.2 Study Endpoints

4.2.1 Primary Study Endpoints

Primary study endpoint will be Blood Oxygen Level Dependent BOLD fMRI signals and Skin Conductance Response (SCR) during recall.

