9.4 Description of Statistical Methods

9.4.1 General Approach

Statistical Methods

SCR Analyses

For all experimental phase, SCR will be computed for each trial by subtracting the mean skin conductance level observed during the last two seconds of context presentation from the maximal skin conductance level reached during CS presentation. All SCR values will be square-root transformed prior to any statistical analyses. To evaluate extinction recall, an extinction retention index (ERI) will be computed for each individual using the following formula: $100 - (\text{mean SCR to the first 4 CS+E trials during recall} / \text{maximum SCR reached during conditioning for this same cue}) * 100$.

Functional MRI analysis

The specific emphasis of the fMRI analysis will be on the extinction recall phase (first four trials of the CS+E vs. first four trials of the CS+U contrast). This contrast has been chosen given the literature demonstrating a significant deficit of PTSD patients during that specific phase of the experimental protocol. BOLD signal will be extracted from the four ROIs (amygdala, dACC, vmPFC and hippocampus). For each of these ROIs, we will use mixed model ANOVAs with time (pre vs. post PE) and group (E2+PE vs. Plc+PE) to investigate main effect of each of these variables as well as group by time interaction. Whole-brain analyses will also be conducted as supplemental analyses for the sake of completeness. We will also conduct regression analyses comparing the change in BOLD responses in each of our ROIs from post- to pre-treatment with PTSD symptom reduction in each of the two groups (E2+PE and Plc+PE).

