9.5 Sample Size

Pre to post treatment assessment using our experimental approach has not been previously conducted, and therefore it is challenging to calculate power to estimate potential sample or effect size comparing the pre to post time-points. The following sample size calculations pertain to the expected changes related the psychophysiological and neurobiological indices to be obtained. The sample size selected for this proposal is based on the detection of between-group significant differences at an alpha of .05 using data collected in our previous study of fear conditioning and extinction recall in controls and patients (PTSD) and using our preliminary fMRI data in women with high (HE) vs. low estradiol (LE) (Zeidan et al, 2011). We have calculated our power to detect between-group differences with a sample size of 25 subjects per group. Based on our previous experience with this population and this paradigm, we expect that (at each of the two time points) it is possible that we will have unusable data in approximately 20% of the subjects due to data of insufficient quality for at least one phase of the experiment. Reasons for this include poor SCR responses, head motion during scanning, or technical difficulties with SCR or fMRI. In addition, we anticipate dropout of ~20 % of patients after the initiation of the study. Thus out of the total of 80 patients, we expect to obtain a full data set (from all time points) from 50 patients. By using the effect size obtained from our previous study (see above), an alpha level of 0.05 and 50 patients, we will have 85% power to detect a significant between-group difference. Regarding the clinical measures, we do not have data to calculate power because of the novelty, but since it is a preliminary proof-of-concept aim, the results to be obtained will help inform future power analyses and calculations for this line of research.

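### At least five primary recall measures are tested at an undivided 0.05 with no success rule, and the adjustment that section 9.4.10 refers to is not in the documents

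*Combined protocol and SAP*

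**What the plan says.** Section 4.2.1 defines the primary endpoint in one sentence: "Primary study endpoint will be Blood Oxygen Level Dependent BOLD fMRI signals and Skin Conductance Response (SCR) during recall". It names no lead measure.

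Section 9.4.1 turns this into several measures. For imaging, "BOLD signal will be extracted from the four ROIs (amygdala, dACC, vmPFC and hippocampus"), and each region is analysed on its own: "For each of these ROIs, we will use mixed model ANOVAs with time (pre vs. post PE) and group (E2+PE vs. Plc+PE"). Main effects and the interaction are all listed. For skin conductance, "an extinction retention index (ERI) will be computed for each individual".

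The only significance level is in 9.5, where the sample size is "based on the detection of between-group significant differences at an alpha of .05". Sidedness is not stated.

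Section 9.4.10 carries the multiplicity heading. It mentions the repeated assessments and then says "We describe the plan of analysis and adjustments in section 10.4.6". Section 10 deals with source documents and has no such subsection. If 9.4.6 was meant, that section covers descriptive statistics, longitudinal models and missing data. Its nearest statement is "we will use established methods for such study designs to examine treatment differences", and it adjusts no significance level.

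The leading test is also left open. Section 3.1 predicts a Time x Group interaction for both SCR and BOLD. The synopsis lists a post-treatment group effect first for BOLD, then within-group changes and the interaction. For SCR it names a group-by-condition interaction.

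**The concern.** A plan with several primary measures needs a rule saying which results, in what combination, meet the primary objective. This plan has none, and the section that should supply it refers to text that is not there. Correcting the section number would not help, because 9.4.6 has no adjustment either.

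The choice of rule matters in both directions. If one positive measure out of five is enough, the chance of a false claim exceeds the nominal level at any correlation below 1. If all five are needed, false claims are controlled, but a power figure for a single comparison overstates the chance of success. A rule chosen after the results are known could follow whichever measure came out positive.

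**Working it through.** **The plan's own figure.** Section 9.5 states 85% power with 50 evaluable patients, 25 per group, at alpha 0.05. It gives no effect size, so the 85% cannot be reproduced directly. Solving backwards with a two-sided two-sample t test at 25 per group, 85% power corresponds to a standardised difference of d = 0.865. That value is our inference.

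**Counting the measures.** One SCR recall measure plus BOLD in four regions gives 1 + 4 = 5. The count is derived and is a minimum. Between-session SCR (Hypothesis 1 in 9.2) and information flow by DCM (Hypothesis 1.1 in 3.1) also appear in the primary hypotheses.

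**Assumptions not in the documents.** Any one significant result counts as success. Each test is two-sided at 0.05. All pairs of test statistics share a correlation ρ, with each measure signed so that positive favours estradiol.

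**Family-wise error, two-sided.** At ρ = 0 it is 1 − 0.95^5 = 0.226. For ρ > 0, with c = 1.96:

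FWER = 1 − ∫ φ(u) [Φ((c − √ρ·u)/√(1−ρ)) − Φ((−c − √ρ·u)/√(1−ρ))]^5 du

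**Counting only results favouring estradiol.** The second Φ term drops out. At ρ = 0 this gives 1 − 0.975^5 = 0.119.

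| Rule: any one of five | ρ = 0 | ρ = 0.5 | ρ = 0.9 | Nominal |
|---|---|---|---|---|
| Either direction | 22.6% | 18.3% | 10.2% | 5% |
| Favouring estradiol only | 11.9% | 9.1% | 5.1% | 2.5% |

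Simulated two-sample t tests at 25 per group gave 22.8%, 18.4% and 10.2% for the first row. If BOLD were a single test, so that there were only two, the two-sided figures would be 9.8%, 9.1% and 7.0%.

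**If all five must be positive.** The false-positive rate cannot exceed that of a single test. Power does fall: if each measure had 85% power and the measures were independent, 0.85^5 = 44%. Positive correlation would raise that figure.

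**Power after adjustment.** Holm's strictest step with five tests is 0.05/5 = 0.01. At d = 0.865 and 25 per group, power for one between-group comparison falls from 85% to 65%.

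If the test is Time x Group, analysed as a change score with equal variances and a group difference only after treatment, then d_change = d/√(2(1−r)). Here r is the pre-post correlation, which the documents do not give:

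| r | d_change | Power at 0.05 | Power at 0.01 |
|---|---|---|---|
| 0 | 0.612 | 56% | 31% |
| 0.3 | 0.731 | 72% | 47% |
| 0.5 | 0.865 | 85% | 65% |
| 0.7 | 1.117 | 97% | 89% |

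**The case against.** The strongest reply is that no section adopts an any-one-counts rule. Section 4.2.1 is written in the singular and joins BOLD and SCR with 'and', so it can be read as requiring both. On that reading error is not inflated. The hypotheses are also directional, so a result favouring placebo would not be claimed as support, and the lower row of the first table is then the relevant one. Both points stand. They limit the size of the problem but do not supply a rule.

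A second reply concerns power. A reader might infer from 9.5, which says "it is challenging to calculate power to estimate potential sample or effect size comparing the pre to post time-points", that the 85% cannot be power for Time x Group. The documents do not settle this. The next sentence of 9.5 ties the calculation to expected changes in the psychophysiological and neurobiological indices, and a change-score analysis has the same 85% power when r = 0.5. A between-group comparison is the more natural reading. The fair request is for the plan to say which test and measure were meant.

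A third reply is that the SCR descriptions need not conflict. The retention index is a summary measure, and group-by-condition and Time x Group terms could sit in one model. That is correct; what is missing is a statement of which one leads.

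A proof-of-concept defence does not reach this point. Section 9.5 uses that description for the clinical measures, and the synopsis labels the trial Phase 3.

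**Conclusion.** The gap is real: at least five primary measures, one undivided 0.05, no success rule, and a promised adjustment that appears nowhere in the documents. It should be closed before unblinding.

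Its size depends on the rule. A reader might infer that the trial has a 22.6% false-positive rate. The documents do not support that, because the figure needs an unstated any-one-counts rule, uncorrelated measures and results counted in either direction. Under the any-one-counts assumption, the supportable range over correlations of 0 to 0.9 is 22.6% down to 10.2% in either direction, or 11.9% down to 5.1% for results favouring estradiol. Under an all-must-be-positive rule there is no inflation, and the open question is then power for trial success.

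The ROI wording in 9.2, which leaves out the hippocampus, and the references to sections 10.1 to 10.3 in 9.4.2 and 9.4.3 are clerical.

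**What to change.** Before unblinding, keep the sentence in 9.4.10 on repeated assessments, replace the reference to 10.4.6, and add one rule. Suggested text:

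> The primary family is five estradiol-versus-placebo comparisons at extinction recall: one named SCR measure already in this plan, and BOLD for CS+E minus CS+U over the first four trials of each, in vmPFC, hippocampus, dACC and amygdala. One named test is used for all five. Holm's procedure controls family-wise error at two-sided 0.05, and a claim is made only for the measures it rejects. All other tests, including between-session SCR, DCM, within-group pre-post and whole-brain analyses, are supportive.

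The sponsor has three choices to make:

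- **Test:** Time x Group, as 3.1 predicts, or the post-treatment group effect that the synopsis lists first.
- **SCR measure:** one of those already described in the plan.
- **Procedure:** Holm, or a fixed testing order starting from one named lead measure, which is equally acceptable.

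The synopsis should then be aligned. Section 9.5 should state which measure and which test the 85% concerns, and that it is power for one unadjusted comparison.

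The cost is a text amendment with no new data. Section 9.4.9 plans no interim analysis and defers analysis to the end of the study, so the rule can still be set without sight of results. Holm costs the power shown in the working. A fixed order costs the lead measure no power, but testing stops at the first non-significant result.
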